14.2.4 All-cause Mortality

All-cause mortality analysis will be based on data collected on the ‘Death’ eCRF page.

All-cause mortality is defined as the proportion of subjects who died during the study, regardless of the cause of death.

Number and proportion of subjects dying through Day 60 and the corresponding two-sided Wilson 95% CI will be provided by treatment groups based on the ITT analysis set.

In case more than 6 deaths are observed, the difference in proportion of each dose to placebo will be presented with two-sided 95% CIs based on the Miettinen-Nurminen method. In addition, summary score estimates of the common difference in proportion, stratified for use of corticosteroids at a prednisone equivalent daily dosage of ≤ 15 mg or > 15 mg within 48 hours prior to randomization, AVT use in the 48h prior to randomization and country will be presented with 95% CIs based on stratified Newcombe confidence limits.

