8.3 Withdrawal from the Study by the Participant

The participant will discontinue the study if:

- Participant withdraws consent, participant's legally authorized representative withdraws consent, or the participant requests discontinuation from the study for any reason.
- Participant dies.
- Participant is lost to follow-up.
- Participants are free to withdraw from the study at any time upon request without any consequence. In the case of a participants becoming lost to follow-up, attempts to contact the participant should be made and documented in the participant's medical records.

After hospital discharge, a participant will be considered lost to follow-up if he or she fails to appear for a follow-up telemedicine conference or in-person assessment at the study site. The study site must attempt to contact the participant and reschedule the missed visit as soon as possible, counsel the participant on the importance of maintaining the assigned visit schedule and ascertain if the participant wants to or should continue in the study.

Before a participant is deemed "lost to follow-up", the Investigator or designee must make every effort to regain contact with the participant: 1) where possible, make 3 telephone calls and 2) if

necessary, send a certified letter (or an equivalent local method) to the participant's last known mailing address. These efforts will be documented in the participant's record.

Participants who withdraw from this study or are lost to follow-up after signing the informed consent form (ICF) and administration of the study intervention will be replaced in Part A only with Sponsor approval. The reason for participant discontinuation from Part A and B of the study will be recorded on the appropriate eCRF.

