10.4.3.2 Analysis of Clinical Status

The number and percentage of participants in each clinical status category will be presented by treatment group and by time point in a graphical manner.

An ordinal logistic regression model will be used to compare the clinical status from Day 1 through Day 60 of M5049 groups to placebo. Under the assumption of proportional odds, a summary odds ratio and its 95% CI will be estimated for each M5049 group versus placebo. A test for the proportionality assumption will also be made.

Separate odds ratios will also be estimated for dichotomized version of the health status:

- Death versus any other category.
- Worsening versus stable/improvement.
- Not discharge versus hospital discharged.

An exploratory longitudinal analysis will be run to account for all of the time points and present estimates of treatment effect by time point.

10.4.3.3 Analysis of Time to SpO₂ of $\geq 94\%$ Sustained for at Least 24 hours in Room Air

The time to response is defined as the time from first dose (Day 1) to the date of the first SpO₂ $\geq 94\%$ sustained for at least 24 hours in room air up to Day 28. For participants who die and those considered as failure (that includes use of mechanical ventilation, ICU admission leading to treatment discontinuation, and relapse) the time to response will be censored at Day 28. For participants completing the study without meeting response or failure, the time to response will be censored at Day 28. Participants withdrawn before the End of Study Visit without meeting response or failure will be censored at the last date of SpO₂ assessment in room air temperature.

Cumulative distribution function for time to response will be estimated via the Kaplan-Meier (product-limit estimates) method by treatment group and presented together with associated statistics (median time to response, response rates at Day 7, Day 14, and Day 28) including the corresponding two-sided 95% CI.

10.4.3.4 Analysis of All-cause Mortality Through Day 60

Number and percentage of death through Day 60 with 95% CI will be presented by treatment group.

10.4.3.5 Analysis of Time to Intensive Care Unit Admission (Day 1 Through Day 28)

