8.1 Definition of Analysis Populations

The analysis populations are specified below. The final decision to exclude participants from any analysis population will be made during a data review meeting prior to database lock and unblinding.

Enrolled Analysis Set

The Enrolled Analysis Set includes all participants who sign informed consent and will be used to report disposition data.

Intent-To-Treat Analysis Set (ITT)

The ITT consists of all treated participants and it will be used for the primary efficacy analysis.

Participants will be analyzed according to the actual treatment received, which will be determined based on the treatment taken just after randomization, as collected in the electronic Case Report Form (eCRF). Occurrences of mistreatment (i.e. a different treatment from the one assigned via randomization) will be evaluated on a case by case basis.

Safety Analysis Set (SAF)

The SAF consists of all participants who received at least one dose of study intervention and is used for evaluation of safety endpoints.

Participants will be analyzed according to the actual treatment received, which will be determined based on the treatment taken just after randomization, as collected in the eCRF. Occurrences of mistreatment will be evaluated on a case by case basis.

Therefore, the ITT and the SAF are the same population and can be used interchangeably.

Pharmacokinetics Analysis Set (PKAS)

The PKAS will include all participants who received at least one dose of active treatment, for whom at least one quantifiable post dose plasma concentration of M5049 is obtained, and without any relevant protocol deviations and absence of factor that may have an influence on PK. It will be used for the evaluation of PK endpoints.

Participants will be analyzed according to the actual treatment received, which will be determined based on the treatment taken just after randomization, as collected in the eCRF. Occurrences of mistreatment will be evaluated on a case by case basis.

Pharmacodynamics Analysis Set (PDAS)

The PDAS will include all participants who received at least one dose of study intervention, for whom at least one post-baseline biomarker result is obtained and without any relevant protocol deviations or events that may have an influence on pharmacodynamics. It will be used for the evaluation of endpoints related to inflammatory and CCI biomarkers.

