9.1 Presentation of continuous and qualitative variables

Continuous variables other than PK will be summarized using the following descriptive statistics, i.e.

- number of subjects with non-missing values (n)
- mean, standard deviation

- median, 25th Percentile - 75th Percentile (Q1-Q3)
- minimum (Min) and maximum (Max)

Missing statistics, e.g. when they cannot be calculated, should be presented as “nd”. For example, if $n=1$, the measure of variability (SD) cannot be computed and should be presented as “nd”.

Qualitative variables will be summarized by counts and percentages.

Mean, median, Q1, Q3, Min, and Max will have the same precision as collected in SDTM datasets for non-derived data. Standard deviation will be presented with 1 digit more than the mean. Percentage and percent change from baseline will be reported using 1 decimal digit, if not specified otherwise.

Unless otherwise stated, the calculation of proportions will be based on the number of subjects in the analysis set of interest. Therefore, counts of missing observations will be included in the denominator and presented as a separate category.

For variables where a subject may have more than one category due to multiple responses per subject (i.e. not mutually exclusive categories), the number of subjects included in each category will be summarized as a percentage from all subjects. Therefore, the total frequency across categories may not equal the total number of all subjects in the population.

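### Day 60 mortality is reported as deaths over all treated participants with no rule for unknown vital status, so the estimate can only err downward

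*SAP*

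**What the plan says.** SAP 14.2.4 defines the endpoint: "All-cause mortality is defined as the proportion of subjects who died during the study, regardless of the cause of death". The estimate follows: "Number and proportion of subjects dying through Day 60 and the corresponding two-sided Wilson 95% CI will be provided by treatment groups", on the ITT set. SAP 8.1 defines that set: "The ITT consists of all treated participants and it will be used for the primary efficacy analysis". Protocol 10.4.3.4 plans the same kind of summary: "Number and percentage of death through Day 60 with 95% CI will be presented by treatment group". Differences from placebo (Miettinen-Nurminen, and stratified Newcombe) are added only if there are more than 6 deaths.

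The general rule in SAP 9.1 is: "Unless otherwise stated, the calculation of proportions will be based on the number of subjects in the analysis set of interest". It adds that "counts of missing observations will be included in the denominator and presented as a separate category". SAP 9.8 analyses data as observed, with listed exceptions that do not include vital status. The SAP modification history says that sensitivity analysis was retained for the primary efficacy endpoint alone.

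Protocol 8.3 allows withdrawal at any time and defines loss after discharge: "a participant will be considered lost to follow-up if he or she fails to appear for a follow-up telemedicine conference" or an in-person assessment. Protocol 8.2 calls for vital status at Days 14, 21, 28 and 60 after treatment is stopped, by phone or telemedicine if needed, unless consent is withdrawn.

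**The concern.** A treated participant with unknown Day 60 status counts in the denominator and not among the deaths. Showing such people in a separate missing category, as SAP 9.1 asks, leaves the percentage and its Wilson interval as they would be if all of them had survived. Unobserved deaths can only be left out, so the error has one direction.

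Mortality is a secondary endpoint, and it bears on the safety of an immunomodulator given during an infection. The plan handles incomplete follow-up elsewhere. SAP 14.2.5 to 14.2.7 count death as an event and censor event-free participants at the earlier of Day 28 and discontinuation, and SAP 14.2.1 has an explicit missing outcome. SAP 14.2.4 has neither, although it runs to Day 60 and so allows more time for loss.

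**Working it through.** **Inputs from the documents.** 15 (Part A) + 135 (Part B) = 150 participants, allocated 1:1:1, so 150/3 = 50 per arm. Estimator: recorded deaths / treated participants. The available text gives no mortality or loss rate for this endpoint (protocol text before 10.3 is redacted), so there is no planned figure to reproduce.

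**Assumptions.** True Day 60 mortality m from 5% to 20%; share lost d from 5% to 20%.

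**Step 1. General form.** Shortfall = (share lost with unknown status) × (risk of death between loss and Day 60). It is never negative.

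**Step 2. Loss unrelated to risk, at a fixed day t.** Take death times as exponential with mean 14 days, truncated at Day 60: F(t) = (1 − e^(−t/14)) / (1 − e^(−60/14)). The shortfall is m × d × (1 − F(t)).
- F(3) = 0.196 and F(21) = 0.788.
- m = 10%, d = 10%: 0.10 × 0.10 × 0.804 = 0.8 point (Day 3); 0.10 × 0.10 × 0.212 = 0.2 point (Day 21).
- m = 10%, d = 20%: 1.6 points (Day 3); 0.4 point (Day 21).

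**Step 3. Check with a second model.** Independent exponential death and loss over 60 days, with rates a = −ln(1 − m)/60 and b = −ln(1 − d)/60. The crude figure is a/(a + b) × (1 − e^(−60(a + b))). If all loss is on Day 1, the shortfall is m × d.

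| m | d | Crude | Shortfall (points) | Shortfall if all lost on Day 1 |
|---|---|---|---|---|
| 10% | 5% | 9.75% | 0.25 | 0.5 |
| 10% | 10% | 9.50% | 0.50 | 1.0 |
| 10% | 20% | 8.98% | 1.02 | 2.0 |
| 20% | 20% | 18.0% | 2.0 | 4.0 |

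**Step 4. Compare with the precision.** The Wilson 95% interval for 5/50 is 4.3% to 21.4%, a width of 17.1 points. The Miettinen-Nurminen interval for 5/50 against 5/50 is −12.9 to +12.9 points.

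**Step 5. Effect on the comparison.** With equal true mortality of 10% and losses of 5% and 15%, the spurious difference is 0.51 point (1.0 if all on Day 1). With 20% mortality and losses of 5% and 20%, it is 1.5 points (3.0).

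**Step 6. Loss related to risk.** If 5 of 50 are lost with a 50% later risk, the shortfall is 5/50 × 50% = 5 points. If 10 of 50 are lost, it is 10 points. The size of the loss does not fix the order of the arms: 10 of 50 lost at 1% risk gives 0.2 point, while 3 of 50 lost at 40% gives 2.4 points.

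**Step 7. What the added outputs would show.** Assume 50 in an arm, 2 early deaths, then k lost, then 2 late deaths. Kaplan-Meier mortality = 1 − (1 − 2/50)(1 − 2/(48 − k)). The worst case is (4 + k)/50.

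| Lost (k) | Crude | Kaplan-Meier | Best to worst case |
|---|---|---|---|
| 2 | 8.0% | 8.2% | 8% to 12% |
| 5 | 8.0% | 8.5% | 8% to 18% |
| 10 | 8.0% | 9.1% | 8% to 28% |

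The planned figure is the same in all three rows and gives no sign that more is unknown in the last.

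**The case against.** The strongest case for leaving the plan alone has five parts.

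- **Follow-up is protected.** Under Protocol 4.6 and 8.2, those who stop treatment return to the schedule and are asked to continue to Day 60. Protocol 8.3 requires repeated contact attempts before anyone is declared lost. Protocol 9.3.7.1 has sites report serious events they learn of after the study. This stands, and it limits the problem to consent withdrawal and true loss. A reader might infer that stopping treatment for tolerability removes a participant from the death count; the documents do not support that.
- **Missing status is to be shown separately.** This is also right. The text does not declare lost participants alive, and SAP 10.1 tabulates premature study discontinuation by reason. But the percentage does not change, and discontinuation from the study is not the same as unknown vital status at Day 60.
- **Mortality is not the exception.** A reader might infer that every other time-dependent outcome uses Kaplan-Meier. That is wrong: relapse and re-hospitalization (SAP 14.2.12 and 14.2.13) are also crude proportions to Day 60.
- **Another death analysis exists.** SAP 14.2.2 compares death with all other categories by logistic regression, without imputation, so unknown status drops out. It is run only if each level has at least 6 participants and yields odds ratios, so it does not repair the mortality estimate by arm.
- **Kaplan-Meier has its own bias.** If the people lost are low-risk and already discharged, it overstates mortality. In Step 7 with 10 lost who all survive, the truth is 8.0% and Kaplan-Meier gives 9.1%. If sicker people leave, it still understates. This stands, and is why the count of unknowns and the bounds are needed beside it.

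The study is also exploratory, without confirmatory testing. That lowers the priority but does not supply the missing rule.

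**Conclusion.** The point holds as a cheap improvement. SAP 14.2.4 has no rule for unknown Day 60 vital status, and its estimate can only err downward. With loss of 10% to 20% unrelated to risk and an assumed 10% mortality, the shortfall is about 0.2 to 1.6 points (2.0 if all 20% leave on Day 1), well inside the sampling error at 50 per arm. It reaches 5 to 10 points only if 5 to 10 of 50 are lost with about a 50% later risk of death. If losses are few and late, the crude and Kaplan-Meier figures nearly agree.

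A reader might conclude that the arm losing more people is always the more understated. That needs similar post-loss risk in the arms, and the counterexample in Step 6 shows it can fail. The comparison with placebo is distorted only when loss or post-loss risk differs between arms. All mortality and loss rates here are assumptions.

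**What to change.** In SAP 14.2.4, keep the crude counts and Wilson intervals, and add:

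1. Kaplan-Meier mortality at Day 28 and Day 60 by arm with 95% CIs (Greenwood variance, log-log scale), from first dose, censoring at the date last known alive.
2. The difference of each dose from placebo in Kaplan-Meier mortality at Day 60, with its 95% CI.
3. The number with unknown Day 60 vital status by arm. State the definition, for example no recorded death and last known alive before Day 53, where the Day 60 window in SAP 9.9 opens.
4. Best- and worst-case bounds by arm, counting all unknowns as alive and then as dead.

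The cost is SAP wording and one or two standard outputs. No new data are needed: SAP 9.5 already uses survival time from first dose as its example of a duration, and SAP 9.7 already relies on the date of last contact.

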5.2 Part B Objectives

| OBJECTIVES | ENDPOINTS (OUTCOME MEASURES) | IAP SECTIONS |
|---|--|---|
| Primary Efficacy | | |
| To evaluate the time to recovery in participants hospitalized due to COVID-19 pneumonia with M5049 compared to placebo. | Time to recovery from Day 1 through Day 28, defined as time from Day 1 to first occurrence of WHO 9-point ordinal scale 3 or less. | 14.1 |
| Primary Safety | | |
| To assess the safety of M5049 compared to placebo. | 
 Incidence of TEAEs, AESIs, TEAEs leading to treatment discontinuation, and SAEs from Day 1 through Day 60. Clinically significant changes in laboratory parameters and ECGs from Day 1 through Day 28. | 
 15.1 15.3 and 15.5 |
| Secondary | | |
| To assess the proportion of participants free of respiratory support with M5049 compared to placebo. | Alive and not requiring supplemental oxygenation (including any supplemental oxygen, noninvasive or mechanical ventilation and ECMO) through Day 28. | 14.2.1 |
| To evaluate the change in clinical status with M5049 compared to placebo. | 
Clinical status from Day 1 through Day 60 (on a 9-point ordinal scale):
 
 0. Uninfected: no clinical or virological evidence of infection. 1. Ambulatory: no limitation of activities. 2. Ambulatory: limitation of activities. 3. Hospitalized, mild disease: hospitalized, no oxygen therapy. 4. Hospitalized, mild disease: oxygen by mask or nasal prongs. 5. Hospitalized, severe disease: noninvasive ventilation or high flow-oxygen. 6. Hospitalized, severe disease: intubation and mechanical ventilation. 7. Hospitalized, severe disease: ventilation + additional organ support – e.g., pressors, RRT, ECMO. 8. Death. | 14.2.2 |
| To assess normalization of oxygenation status with M5049 compared to placebo in participants who are alive and not on mechanical ventilation. | 
Time to SpO₂ of ≥ 94% sustained for at least 24 hours in room air from Day 1 through Day 28.
 
Further referred as “time to SpO₂ improvement”
 | 14.2.3 |

| OBJECTIVES | ENDPOINTS (OUTCOME MEASURES) | IAP SECTIONS |
|---|--|--|
| To evaluate the numbers of deaths with M5049 compared to placebo. | All-cause mortality (Day 1 through Day 60). | 14.2.4 |

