14.2.2 Clinical Status

Clinical status will be based on data collected on the ‘Ordinal Scale for Clinical Status’ eCRF page and is assessed with the following ordinal scale:

0. Uninfected: no clinical or virological evidence of infection.
1. Ambulatory: no limitation of activities.
2. Ambulatory: limitation of activities.
3. Hospitalized, mild disease: hospitalized, no oxygen therapy.
4. Hospitalized, mild disease: oxygen by mask or nasal prongs.
5. Hospitalized, severe disease: noninvasive ventilation or high-flow oxygen.
6. Hospitalized, severe disease: intubation and mechanical ventilation.
7. Hospitalized, severe disease: ventilation + additional organ support – e.g., pressors, RRT, ECMO
8. Death.

In case of death, the participant will be counted with the clinical status =8 (death) for any scheduled timepoint after death date. There will be no imputation of missing data.

Clinical status is expected every day during hospitalization and then at every scheduled visit after discharge. Day 1 assessment will serve as baseline measurement. If missing, the last non-missing measurement prior to randomization will be used.

The number and percentage of participants in each clinical status category as well as summary statistics for absolute and change from baseline status will be presented by treatment group, in a tabular and graphical form, using a stacked bar chart.

A cumulative logit model will be used to compare the clinical status results of each M5049 group versus placebo at the following analysis visits: Day 7, Day 14, Day 21, Day 28, Day 44 and Day 60 according to the ordinal scale described above. Under the assumption of proportional odds, the odds ratio (OR) and its 95% Wald CI will be estimated for each M5049 group versus placebo. A score test for the proportional odds assumptions will be reported.

Should the model fail, due to an insufficient number of observations per category of the dependent variable, then relevant categories may be collapsed.

In addition, the following dichotomized versions of the clinical status will be derived, only if at least 6 participants in each level are present:

- Death (clinical status = 8) versus any other category (clinical status \neq 8)
- Worsening (clinical status \geq 5) versus stable/improvement (clinical status $<$ 5)
- In-hospital (clinical status \geq 3) versus hospital discharged (clinical status $<$ 3).

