14.2.12 Occurrence of Relapse

Occurrence of relapse analysis will be based on data collected on the 'Date of Visit' eCRF page.

Relapse is defined as a participant who has been discharged from the hospital with an SpO₂ of $\geq 94\%$ sustained for at least 24 hours in room air, but who must be readmitted before or on Day 60, due to either or both the following conditions:

1. Worsening oxygenation (an SpO₂ < 94% in room air), with a positive result of respiratory pathogenic nucleic acid test;

2. Worsening oxygenation (an SpO₂ < 94% in room air), with a worsening lesion on chest imaging (i.e., compared to the participant's chest X-ray or computed tomography at discharge)

Number and proportion of subjects with relapse during the study period (if first discharged) and the corresponding two-sided Wilson 95% CI will be provided by treatment group based on the ITT analysis set.

In case more than 6 events of relapse are observed, the difference in proportion of each dose to placebo will be presented with two-sided 95% CIs based on the Miettinen-Nurminen method. In addition, summary score estimates of the common difference in proportion, stratified for use of corticosteroids at a prednisone equivalent daily dosage of ≤ 15 mg or > 15 mg within 48 hours prior to randomization, AVT use in the 48h prior to randomization and country will be presented with 95% CIs based on stratified Newcombe confidence limits for the differences in proportions.

[figure not shown]

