14.2.13 Occurrence of Re-hospitalization due to COVID-19 Complications

The analysis of occurrence of re-hospitalization due to COVID-19 complications will be based on data collected on the 'Hospitalization' eCRF page.

Re-hospitalization is defined as a participant who has been discharged from the hospital with an SpO₂ of $\geq 94\%$ sustained for at least 24 hours in room air, but who must be readmitted before or on Day 60, for COVID-19 related complications.

Number and proportion of subjects with re-hospitalization due to COVID-19 during the study period (if first discharged) and the corresponding two-sided Wilson 95% CI will be provided by treatment group based on the ITT analysis set.

In case more than 6 events of re-hospitalization are observed, the difference in proportion of each dose to placebo will be presented with two-sided 95% CIs based on the Miettinen-Nurminen method. In addition, summary score estimates of the common difference in proportion, stratified for use of corticosteroids at a prednisone equivalent daily dosage of ≤ 15 mg or > 15 mg within 48 hours prior to randomization, AVT use in the 48h prior to randomization and country will be presented with 95% CIs based on stratified Newcombe confidence limits for the differences in proportions.

CCI

15 Safety analysis

Safety analyses will be done on the SAF analysis set and according to the actual treatment received (see Section 8.1).

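### With 6 or fewer deaths, SAP 14.2.4 gives per-arm figures only and no mortality difference or confidence interval against placebo

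*SAP*

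**What the plan says.** SAP 5.2 states the mortality objective as a comparison: "To evaluate the numbers of deaths with M5049 compared to placebo". Protocol 3.2 has the same objective.

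SAP 14.2.4 has two layers. The first is unconditional: "Number and proportion of subjects dying through Day 60 and the corresponding two-sided Wilson 95% CI will be provided by treatment groups". The second is conditional: "In case more than 6 deaths are observed, the difference in proportion of each dose to placebo will be presented". The difference is to carry two-sided 95% Miettinen-Nurminen intervals. A stratified Newcombe estimate (steroid use, antiviral use, country) follows the same condition. The scope of the count is not given.

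The same switch is used for relapse in 14.2.12 ("In case more than 6 events of relapse are observed, the difference in proportion of each dose to placebo will be presented") and for re-hospitalization in 14.2.13 ("In case more than 6 events of re-hospitalization are observed").

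Protocol 10.4.3.4 asks for less: "Number and percentage of death through Day 60 with 95% CI will be presented by treatment group". The between-arm difference is therefore an addition made by the SAP.

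SAP 14.2.2 has a second analysis of death, an odds ratio for death versus any other category, each dose against placebo. Its condition is different: "the following dichotomized versions of the clinical status will be derived, only if at least 6 participants in each level are present".

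**The concern.** Whether the mortality difference is reported depends on the result, namely the number of deaths. The SAP gives no reason for the threshold. A threshold makes sense for the stratified estimate, where three factors split few events over many cells. It has no such basis for the simple difference, because a score interval such as Miettinen-Nurminen can be computed with a zero cell. SAP 14.2.1 uses that method for the proportion alive without oxygen and sets no event threshold.

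Mortality is a key harm outcome for an immunomodulator given during an infection. If deaths are few but fall on one dose, the section meant to address the mortality objective would show three separate Wilson intervals and no estimate of the difference.

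**Working it through.** **Nothing to reproduce.** The threshold has no stated derivation, and the visible text gives no assumed mortality rate. The check is therefore of the rule's consequences.

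**Inputs**
- 150 participants in total, randomised 1:1:1 (Protocol 4.1): 150 / 3 = 50 per arm.
- Two-sided 95% intervals (SAP section 9).
- Threshold: more than 6, that is, 7 or more (SAP 14.2.4).
- Mortality rates: not given, so assumed and shown as a range.

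**Interval.** The Miettinen-Nurminen limits are the values d that solve (p1 − p2 − d) / √V(d) = ±1.96. Here V(d) = [q1(1 − q1)/50 + q2(1 − q2)/50] × 100/99, and q1 and q2 are the maximum-likelihood estimates restricted to q1 − q2 = d.

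| Deaths, dose v placebo | Difference (points) | 95% CI (points) | Fisher two-sided p | Presented in 14.2.4 if no other deaths? |
|---|---|---|---|---|
| 4 v 0 | 8.0 | 0.5 to 18.9 | 0.117 | No |
| 5 v 0 | 10.0 | 2.4 to 21.4 | 0.056 | No |
| 6 v 0 | 12.0 | 4.4 to 23.9 | 0.027 | No |
| 4 v 1 | 6.0 | −3.5 to 17.2 | 0.362 | No |
| 5 v 1 | 8.0 | −1.8 to 19.7 | 0.204 | No |
| 6 v 1 | 10.0 | −0.1 to 22.2 | 0.112 | Yes (7 deaths) |

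The intervals for 4, 5 and 6 v 0 exclude zero. With 1 placebo death, 4 v 1 and 5 v 1 do not. Fisher's test falls below 0.05 only for 6 v 0.

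**Scope of the count.** The 0-placebo rows are withheld whether the count is trial-wide or per comparison. Deaths on the other dose matter only under the trial-wide reading: 4 on one dose with 3 elsewhere makes 7, and the difference is then shown.

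**How often the count is 6 or fewer.** P(total ≤ 6) for Binomial(150, p), with p assumed:

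| Mortality | 2% | 3% | 4% | 5% | 6% | 8% | 10% |
|---|---|---|---|---|---|---|---|
| P(total ≤ 6) | 97% | 83% | 61% | 37% | 20% | 4% | 0.6% |

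**How often the one-sided pattern arises.** With 10% mortality on one dose and 2% on the other two arms, P(4 to 6 deaths on that dose and total ≤ 6) is 22%. Requiring 0 placebo deaths as well makes it 13%. That second probability is 2.3% for 12% v 4%, 1.2% for 10% v 5% and 0.6% for 15% v 5%.

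**What else in the SAP involves death**
- 14.2.2 odds ratio: needs at least 6 participants in each level, so it is absent at 4 or 5 deaths. At exactly 6 it is planned while the 14.2.4 difference is not. With 0 placebo deaths the logistic estimate is not finite, so the Wald interval gives nothing usable.
- 14.2.2 cumulative logit model: death is category 8 of nine, mixed with the other states.
- 14.2.5 to 14.2.7: death counts as an event together with ICU admission or ventilation, and only to Day 28. Mortality is assessed to Day 60.
- 15.1.1 and 15.2.1: deaths and fatal adverse events are tabulated without a difference.

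**The case against.** The strongest reply is that little is lost. Counts, proportions and Wilson intervals are always shown for every arm beside placebo (6/50: 5.6% to 23.8%; 0/50: 0% to 7.1%), and anyone can compute the difference from them. Protocol 10.4.3.4 asks for no difference, so no requirement is breached. The study is exploratory. The examples with intervals above zero all have no placebo deaths, and the gap matters mainly if background mortality is low. The thresholds in 14.2.2 and 14.2.4 belong to different analyses and need not agree.

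Most of this stands, and it limits the point. A reader might infer that an excess of 4 to 6 deaths on one dose is never compared with placebo. The documents do not support that: the per-arm figures are always side by side, death enters the ordinal model and the ICU and ventilation comparisons, the odds ratio is planned at exactly 6 deaths, and deaths elsewhere can lift the count above the threshold. A reader might also take the threshold as a trial-wide total. That is a reasonable reading, but it is not in the text.

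The reply does not supply a reason for the condition. The SAP chose to add the difference, the objective is comparative, and the method does not need the events. That a reader could compute the interval shows how little it would cost to print it.

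**Conclusion.** The point holds in limited form. At 6 or fewer deaths, with the scope of that count unstated, SAP 14.2.4 gives no mortality difference or interval against placebo, and no other planned analysis reliably provides one. With 50 per arm, this withholds intervals of 0.5 to 18.9, 2.4 to 21.4 and 4.4 to 23.9 points for 4, 5 and 6 v 0 when there are no other deaths.

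These intervals should not be read as established harm. Fisher's test is below 0.05 only for 6 v 0, and one placebo death brings zero into the interval for 4 v 1 and 5 v 1. The argument is for showing the estimate, not for claiming significance.

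The practical weight depends on a mortality rate that the visible text does not give: the rule would usually bite at 2% to 4% and rarely at 8% or more. No corresponding calculation was made for relapse or re-hospitalization, which are included for consistency. This is a cheap improvement to an exploratory plan, not a breach of the protocol.

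**What to change.** In SAP 14.2.4, remove the event condition from the unstratified analysis, so that each dose minus placebo is always presented with its Miettinen-Nurminen 95% interval beside the per-arm figures. Make the same change in 14.2.12 and 14.2.13 for consistency. Keep a threshold only for the stratified Newcombe estimate, and state whether it counts events over the trial or over the two arms compared. Either align it with the condition in 14.2.2 or say why the two differ.

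The cost is a wording change and one table for each of the three endpoints. No new data are needed. The downside is that intervals will be wide when counts are low.
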